4.4 END OF STUDY DEFINITION

A participant is considered to have completed the study if he or she has completed all phases of the study including the last visit (month 18) shown in the Schedule of Activities (SoA), Section 1.4.

The end of the study is defined as completion of the last visit or procedure shown in the SoA in the last study participant.

5 STUDY POPULATION

5.1 INCLUSION CRITERIA

In order to be eligible to participate in this trial, an individual must meet all of the following criteria:

1. Provision of signed and dated informed consent/assent form
2. Stated willingness to comply with all study procedures and availability for the duration of the study
3. Male or female, aged 14-45 years
4. Have an ACL tear diagnosed by a physician
5. Scheduled to undergo ACL reconstruction with any type of autograft (i.e. , a graft of tissue from one point to another of the same individual's body)
6. Patient receiving physical therapy at a MedSport facility

5.2 EXCLUSION CRITERIA

An individual who meets any of the following criteria below will be excluded from participation in this study.

Exclusion Criteria at time of screening:

1. Previous major surgery to either knee
2. Patients who experience a knee dislocation (prior to or in conjunction with the ACL tear)
3. Female volunteers who are pregnant or planning to become pregnant during the study period
4. Patients who cannot undergo an MRI (e. g. metal in body)

Exclusion Criteria at time of randomization:

1. Bony fracture accompanying the ACL injury
2. Multi-ligament reconstruction at the time of the ACLR

5.3 LIFESTYLE CONSIDERATIONS

Not applicable

5.4 SCREEN FAILURES

Screen failures are defined as participants who consent to participate in the clinical trial but are not subsequently randomly assigned to the study intervention or entered in the study. A minimal set of screen failure information is required to ensure transparent reporting of screen failure participants, to meet the Consolidated Standards of Reporting Trials (CONSORT) publishing requirements and to respond to queries from regulatory authorities. Minimal information includes demography, screen failure details, eligibility criteria, and any serious adverse event (SAE).

5.5 STRATEGIES FOR RECRUITMENT AND RETENTION

- **Patients:** Approximately 150 patients (10 of which will be removed from analysis due to the COVID-19 pandemic) will be recruited without regard to gender, race or ethnicity. Potential participants must be between 14-45 years of age.
- **Anticipated accrual rate:** 30 patients per year
- **Anticipated number of sites:** 1
- **Source of participants:** Our primary source of participants will come from Michigan Medicine (in particular MedSport).
- **Recruitment venues:** Michigan Medicine, Local Physical Therapy Clinics
- **How potential participants will be identified and approached:** To identify potential participants, we will examine electronic medical records from MedSport, which is part of Michigan Medicine, for patients who have been diagnosed with an ACL tear. Our study coordinator will examine the record for any exclusion criteria that may also be listed. Once a potential participant is identified, we will approach the patient at a scheduled appointment with their orthopedic surgeon. At this appointment, the coordinator will provide information about the study, gauge patient interest in participating, and confirm eligibility. If the potential participant expresses interest in participating we will follow-up with a phone call or email within 3 days to schedule a pre-operative/baseline testing session.
- **Recruitment strategies:** Direct recruitment through Michigan Medicine, Flyers in local physical therapy clinics in Ann Arbor, Flyers around University of Michigan campus, clinicaltrials.gov
- **Subject retention:** In regard to subject retention, every effort will be made by the study team to achieve optimal retention of participants. We deliver study interventions at a time that corresponds with participants' regularly scheduled physical therapy visits (i.e., they are already in our clinic for treatment and we simply schedule their intervention to coincide with their existing appointment). This has led to 100% subject retention in our pilot work. Retaining subjects at the 9-month data collection time point should not be problematic as patients are still reporting to the clinic at that time (or have just completed therapy and thus are easily accessible to study staff). We will schedule the 9-month appointment time at the time of their last intervention session and follow-up with an email and postcard reminder 2 weeks prior to that appointment. Additionally, we will follow-up with an email 2 days prior to the scheduled appointment to confirm attendance. Similar procedures led to 100% retention in our pilot trial. For the 18-month time point, phone and email contact will be made with subjects or their parents or guardians (if applicable) one month prior to our goal date for testing. When participants are reached, we will schedule a time for an MRI and a separate time to come to MedSport for X-rays, as well as strength/biomechanical testing. Reminders will be emailed and mailed to participants

10 days prior to their scheduled test dates and emailed again at 2 days prior to the test date. In our prior trial, we approached select patients in a similar manner at one-year post-ACLR and 95% agreed to return for follow-up.

- **Subject Incentives:** Participants will receive \$25/week for undergoing study interventions (16 weeks x \$25 = \$400) (groups randomized to receive interventions only). All Participants (randomized and SOC control) will receive \$10/hour for each hour of study testing in which they participate. If the participant is a minor, the minor will receive the incentive.

6 STUDY INTERVENTION

6.1 STUDY INTERVENTION(S) ADMINISTRATION

6.1.1 STUDY INTERVENTION DESCRIPTION

The following study interventions will be administered in addition to standard of care ACL rehabilitation as prescribed by the operating physician. Note that the SOC control group will not receive study interventions; they will only receive standard of care ACL rehabilitation.

Neuromuscular electrical stimulation (NMES): This study intervention will be delivered using the Vectra Neo (DJO Global, Vista, CA)

Eccentric Exercise: Eccentric exercise will be delivered using a BLAST!™ Leg Press System (BioLogic Engineering).

6.1.2 DOSING AND ADMINISTRATION

Neuromuscular Electrical Stimulation: Participants randomized into the NMES + ECC will receive NMES 2x/week for 8 weeks following ACLR, beginning 0-2 weeks post-operative. For the first two weeks, NMES will be delivered in the clinic by the participants' physical therapist. The treatment intensity for the first two weeks will be set to the maximum tolerated by the participant, but all other stimulation parameters will remain as outlined below for the remaining 6 weeks. For the last 6 weeks of NMES treatment, participants will be positioned in a dynamometer with their hips flexed to 90° and ACL knee flexed to 60°. Stimulating electrodes will be placed over the vastus lateralis proximally and the vastus medialis distally. A Chattanooga stimulator (Vectra Neo) will be set to deliver a 2500 Hz alternating current, modulated at 75 bursts/s, with a ramp-up time of 2-seconds, followed by a 50-second rest period. Fifteen isometric actions lasting 10 seconds each will be elicited during each session. The treatment intensity will be set at a minimum intensity (higher if tolerated) to achieve a maximum voluntary isometric quadriceps contraction (MVIC) in the injured limb that is equivalent to an MVIC of 40% of the contralateral side. **Dose Changes:** During the last 6 weeks of NMES treatment intensity will be set at the beginning of each week to ensure strength gains are considered throughout the study. The study team will consider a dose change if the participant cannot tolerate the electrical stimulation. If this were to occur, the physical therapist in charge of the intervention would determine the maximum amount of electrical stimulation tolerable by the participant and determine the percentage of the MVIC from the contralateral, uninjured limb this stimulation would produce.

NMES placebo. Participants randomized to NMES placebo + ECC placebo will receive an NMES placebo intervention 2x/week for 8 weeks following ACLR, beginning 0-2 weeks post-operative (to mimic the timing associated with the NMES intervention). Similar to the NMES intervention group, for the first two weeks NMES will be delivered in the clinic by the participants' physical therapist. The treatment intensity for the first two weeks will be set to the maximum tolerated by the participant, but all other stimulation parameters will remain as outlined below for the last 6 weeks. The NMES placebo will utilize the same equipment and follow the same protocol as in the actual NMES intervention, with the exception that the intensity of the current will be set lower. The treatment intensity will be set at an intensity to achieve a MVIC of 15% of the injured side.

High-Intensity Eccentric Exercise (ECC): Participants randomized into the NMES + ECC group will receive ECC 2x/week for 8 weeks, beginning between 6 - 10 weeks post-ACLR when adequate quadriceps control is achieved. To perform the ECC, participants will be positioned in a BLAST!™ Leg Press (BioLogic Engineering Inc.) with their ACLR knee range of motion limited to 20 to 60° of knee flexion. Participants will perform warm-up trials consisting of 10 concentric and eccentric quadriceps actions with the ACLR limb. Following the warm-up trial, each participant will perform 10 isokinetic eccentric/concentric quadriceps actions with the ACLR limb. In total for each session, patients will complete 4 sets of 10 eccentric/concentric actions with 2-minute rests between each set. During the eccentric actions, participants will train at an intensity equal to or greater than 70-90% of their concentric one-repetition maximum (this will be recorded at the beginning of each week). Concentric intensity will be set at 40% of the one-repetition maximum. **Dose Changes:** Treatment intensity will be set at the beginning of each week to ensure strength gains achieved during the study period are reflected in the dose delivered. The timing of initiation eccentric exercise will be evaluated on a patient-by-patient basis. It will begin when the patient has adequate quadriceps control to handle this type of training and will be determined by the physical therapist working with the participant and their physician.

ECC placebo: Participants randomized to NMES placebo + ECC placebo will receive an ECC placebo intervention 2x/week for 8 weeks, beginning at 6 - 10 weeks following ACLR. ECC placebo will utilize the same equipment and follow the same protocol as in the actual eccentric intervention, with the exception that participants will train eccentrically at 10% of their MVIC.

6.2 MEASURES TO MINIMIZE BIAS: RANDOMIZATION AND BLINDING

Procedures for assignment to a study group: Participants in the treatment groups will be allocated to one of the two study arms using minimization^{38,39}, a method of unbiased allocation ensuring balance across confounding factors. This approach is selected over the more common random permuted blocks within stratum design because of the importance of controlling for two known confounders (1) meniscal injury and treatment and (2) articular cartilage injury – that have $4 \times 3 = 12$ combinations. Some of these combinations are relatively rare (e. g. meniscal tear left intact) which would result in potential imbalance (and subsequent loss of power) among the study arms. We will also include graft type (bone-patellar tendon-bone or quadriceps tendon, hamstring,) and sex as minimization factors. A secure web-based application developed by the Data Coordinating Center will be used by the research coordinator to enter participant information (e. g. , participant ID, minimization factors) and to obtain the assigned study arm.

The following definitions of meniscal tears/treatment will be used for minimization: 1) normal/intact; 2) torn/excision (partial or complete); 3) torn/repaired; 4) torn/left intact. Articular cartilage injury will be defined using the Modified Outerbridge Scale and used in minimization as follows: 1) grade 1 (normal or soft); 2) grade 2 (partial thickness lesions); and 3) grade 3 and 4 (full-thickness lesions).

Blinding. Considerable care will be taken to ensure fidelity of blinding. Study staff will have standardized scripts to describe treatment arms to participants in order to prevent different treatment expectations. Study staff collecting outcome measures will not be aware of treatment assignment. Physical therapists, delivering the interventions, will be provided with treatment allocation from the DCC. Blinded data reviews will be done and the statistical analysis plan will be written prior to database lock and unblinding of statisticians.

6.3 STUDY INTERVENTION COMPLIANCE

Treatments will be delivered in person, so we will be able to directly monitor adherence. Adherence will be quantified as a count variable defined as the total number of sessions completed relative to the number of session prescribed (32 sessions total: 16 of both NMES and ECC or corresponding placebos). We will also use CRFs to record the percentage of MVIC that the NMES treatment produced in each session, as well as the intensity of the eccentric contractions during ECC sessions. We will then determine the number of session participants trained at the recommended dosage relative to the number of sessions recommended (32 total) to have an assessment of dosage adherence.

6.4 CONCOMITANT THERAPY

All participants in this trial will be undergoing standard anterior cruciate ligament rehabilitation as prescribed by their physician and delivered by their physical therapist. Physical therapists will record the components of the standard rehabilitation delivered at each visit for entry in the study database. Eccentric exercise will not be a part of standard of care rehabilitation. While low-intensity NMES is generally considered to be part of ACLR standard of care rehabilitation, all study participants will receive NMES regardless of group assignment and thus any additional treatment with NMES is not warranted. The experimental NMES intervention will be of high intensity, while the placebo NMES will be of low intensity. The low-intensity NMES used for our placebo is generally what is used in standard of care ACL rehabilitation.

7 STUDY INTERVENTION DISCONTINUATION AND PARTICIPANT DISCONTINUATION / WITHDRAWAL

It is critical to the integrity of this study that participants adhere to the visit schedule outlined in the protocol. As such, every reasonable effort should be made to convey the importance of remaining on the study to the participants.

7.1 DISCONTINUATION OF STUDY INTERVENTION

Study interventions may be discontinued for any of the following reasons:

- Unacceptable toxicity (this may include serious adverse events [SAEs] related to study treatment)
- Participant request or withdrawal of consent
- Pregnancy
- Investigator discretion

In instances where participants elect to discontinue NMES treatment per protocol, the following procedure will be followed:

- 1) Participant will be asked if they would be willing to continue with NMES at a maximum tolerated dosage. If yes, patient will continue trial with NMES at this revised dosage. If no, go to #2.
- 2) Participant will be asked if they would be willing to continue with the ECC treatment only (i.e., discontinue NMES, but remain in the study and only receive ECC per protocol). If yes, participant will continue in trial only completing ECC. If not, go to #3
- 3) Participant will be asked if they would be willing to continue being followed to gather study-related measurements, but receive no study-related interventions. If yes, participant will continue in trial only being measured as outlined in the study protocol. If no, participant will be withdrawn from the study as requested.

Consistent with the intention-to-treat principle, randomized participants who permanently discontinue study interventions will continue in the study, and remaining study procedures may be completed as indicated by the study protocol. The data to be collected at the time of study intervention discontinuation will include the following:

- In any participant who does not complete study interventions, we will attempt to gather MRI, strength, and biomechanical data at the 18 month study time-point. Of note, these participants will not be considered SOC control group participants for future study conduct or analyses.

7.2 PARTICIPANT DISCONTINUATION/WITHDRAWAL FROM THE STUDY

Participants are free to withdraw from participation in the study at any time upon request.

An investigator may discontinue or withdraw a participant from the study for the following reasons:

- Pregnancy
- Significant study intervention non-compliance

- If any adverse event (AE), or other medical condition or situation occurs such that continued participation in the study would not be in the best interest of the participant
- If the participant meets an exclusion criterion (either newly developed or not previously recognized) that precludes further study participation
- Participant is unable to tolerate study intervention dosage
- Due to COVID-19, or any other pandemic crisis

The reason for participant discontinuation of study intervention will be recorded on the Treatment Status Case Report Form (CRF). Withdrawal from the study will be recorded on the Final Status CRF. Participants who were discontinued from treatment due to COVID-19 or other pandemic crisis may be replaced.

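### Section 7.2 allows withdrawal from the study for intolerance or non-compliance while Section 7.1 keeps discontinuers in it, and for stops outside the NMES steps 7.1 names no 9-month strength test

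*Combined protocol and SAP*

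**What the plan says.** Section 7.2 opens its list with "An investigator may discontinue or withdraw a participant from the study for the following reasons". Two entries concern the intervention rather than the person's availability for measurement: "Significant study intervention non-compliance" and "Participant is unable to tolerate study intervention dosage". The paragraph below the list keeps the two events apart. The reason for stopping the intervention goes on the Treatment Status CRF, whereas "Withdrawal from the study will be recorded on the Final Status CRF".

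Section 7.1 takes the other line. Under intention-to-treat, randomized participants who permanently stop the interventions "will continue in the study, and remaining study procedures may be completed as indicated by the study protocol". For participants who elect to stop NMES it sets out three steps: a tolerated dosage, then ECC alone, then measurement alone. On the third step it says "If yes, participant will continue in trial only being measured as outlined in the study protocol". For anyone who does not complete the interventions, its list of data to be collected has a single item: "we will attempt to gather MRI, strength, and biomechanical data at the 18 month study time-point".

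Section 6.1.2 adds that a dose change is considered when NMES cannot be tolerated. Section 3 makes the changes to 9 and to 18 months in isokinetic quadriceps strength symmetry co-primary. Section 9.3 defines the mITT set as everyone randomized who received at least one intervention. Section 9.4.2 handles missing outcomes by multiple imputation, starting from missing at random, with nonignorable methods optional.

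**The concern.** Intolerance and non-compliance are reasons to alter or stop treatment. Neither in itself prevents a later strength test. If either is used to end study participation, the co-primary outcome is lost for a reason connected with treatment.

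Such losses could differ by arm. Section 4.3 sets a lower current in the placebo arm after the first two NMES weeks, the ECC intensities also differ by arm, and Section 2.3.1 expects NMES discomfort. If the participants concerned also recover less strength than baseline data predict, imputation under missing at random does not fully correct for their absence. A SAP finalized before unblinding can model missing values but cannot recover a 9-month test that was never done.

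**Working it through.** **1. Which stops are covered**

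| Situation | Retention route | 9-month strength test |
|---|---|---|
| Participant elects to stop NMES and accepts follow-up | 6.1.2 dose change; 7.1 steps 1 to 3 | Kept: step 3 follows the protocol's measurements, which include Testing Visit 4 (1.4, 8.1) |
| Participant stops ECC | 7.1 general rule only | Allowed, not required, not named |
| Investigator stops treatment | 7.1 general rule only | Allowed, not required, not named |
| Investigator withdraws from the study under 7.2 | None stated | Lost |

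The NMES steps do not bar the last row.

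**2. The plan's own figure.** Section 9.2 uses 56 per arm, 20% drop-out, effect size 0.7 and two-sided alpha 0.025. 56 × 0.8 = 44.8, or 45 per arm. Power by noncentral t is 84.9%, so the stated minimum of 80% holds. It falls just below 80% (79.9%) only at about 28% total loss, 40 per arm. Power is not the issue.

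**3. Bias if withdrawn participants are not measured.** Let e_A and e_P be the fractions withdrawn in the active and placebo arms, and let g be how many SD worse they are than the others, unexplained by covariates.

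Bias = g × (e_A − e_P), with a positive value favouring NMES + ECC.

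The documents give neither e_A, e_P nor g, so all are assumed. For 15% vs 10%: 0.25 × 0.05 = 0.0125 SD and 1.0 × 0.05 = 0.05 SD.

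**4. Effect on test size.** Simulation with 56 per arm, no true effect, 20% total loss per arm, a linear model on treatment and baseline (assumed baseline–outcome correlation 0.5), two-sided 0.025, and 40,000 replicates per scenario:

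| Withdrawn, active / placebo | g | Bias (SD) | Size |
|---|---|---|---|
| 15% / 10% | 0.25 | 0.013 | 0.026 |
| 15% / 10% | 1.0 | 0.050 | 0.031 |
| 10% / 5% | 0.25 | 0.012 | 0.025 |
| 10% / 5% | 1.0 | 0.049 | 0.030 |
| 10% / 10% | 1.0 | −0.001 | 0.024 |
| 5% / 20% | 1.0 | −0.150 | 0.076 |
| 10% / 0% | 1.0 | 0.101 | 0.047 |
| 20% / 0% | 1.0 | 0.200 | 0.122 |

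Analytic check: SE = √(2/45) × √0.75 = 0.183 SD and the critical value t(87; 0.9875) is 2.281. A bias of 0.05 SD gives noncentrality 0.05/0.183 = 0.27 and size 0.030; a bias of 0.10 SD gives 0.047. Both agree with the table. The smallest significant difference is 2.281 × 0.183 = 0.42 SD.

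**5. Imputation and measurement.** Multiple imputation on treatment and baseline alone leaves the bias nearly unchanged: 0.054 SD for 15% vs 10% and 0.097 SD for 10% vs 0%, both at g = 1. Auxiliary data, such as strength at Testing Visits 2 and 3, would shrink it by whatever part of g they capture. If all withdrawn participants are measured, bias is within 0.003 SD of zero and size is 0.023 to 0.026. If half are measured, the 10% vs 0% bias at g = 1 falls to about 0.05 SD.

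**The case against.** The strongest reply is that the two sections can be read together. Section 7.2 is discretionary, covers both discontinuing and withdrawing, and is followed by separate records for each. Section 7.1 can then be taken as the general rule. This stands in part. A reader might infer that 7.2 orders intolerant participants out of the study, or that 7.1 drops their 9-month visit. The documents support neither. Section 7.1 permits the remaining scheduled procedures, Testing Visit 4 is among them, and the 18-month item does not say that other visits stop. What remains is a discretion with no stated limit beside a contrary intention-to-treat rule.

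Second, NMES intolerance meets two retention routes first (6.1.2 and the 7.1 steps), and the documents' evidence of discomfort concerns NMES, not ECC. That lowers the likely number affected. It does not cover ECC stops or prevent investigator-initiated withdrawal.

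Third, retention may be good. Section 5.5 reports 100% in pilot work, and 95% of selected patients agreed to return at one year. Sections 7 and 7.3 require retention efforts, though these address participants who might leave or miss visits rather than those an investigator withdraws. The plan still budgets for 20% drop-out.

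Fourth, Section 9.4.2 names differential follow-up as a ground for nonignorable methods, does not exclude auxiliary data, and leaves details to the SAP. That is fair, and it is why no change to the analysis is asked for.

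**Conclusion.** The point holds as an unreconciled conflict and an avoidable gap in collecting co-primary data. It is minor to moderate.

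Size and direction are unknown. The documents give no withdrawal rates by arm and do not say whether the withdrawing investigator knows the allocation. Under the moderate assumptions (5 percentage points between arms, g of 0.25 to 1.0) bias is about 0.01 to 0.05 SD, against a planned effect of 0.7 SD, and size is 0.025 to 0.031. Equal rates give none; higher withdrawal on placebo biases against NMES + ECC.

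A reader might infer from the 0.122 row that the trial's type I error is seriously at risk. The documents do not support that. The row needs all of a 20% active-arm loss to be such withdrawals, none on placebo, a full 1 SD deficit, and no covariate or auxiliary information about it.

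**What to change.** 1. Reconcile Sections 6.1.2, 7.1 and 7.2 so that non-compliance or intolerance, however treatment is then managed, does not by itself end outcome follow-up. Record study withdrawal for these reasons on the Final Status CRF only if the participant withdraws consent for follow-up or the best-interest provision in 7.2 applies.

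2. In Section 7.1, name both the 9-month and the 18-month strength tests for randomized participants who do not complete the interventions, and state that the remaining procedures will be sought rather than that they may be done. Except those who withdraw consent for follow-up, those to whom the best-interest provision applies, and those whose follow-up ends under the pregnancy provisions. Sections 7.1, 7.2 and 8.3.10 differ on pregnancy and must themselves be reconciled.

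This proposes no rule for stopping treatment or changing dose. The cost is protocol wording and the effort of pursuing a few visits already scheduled, with no new form or procedure. The estimated effect may be slightly smaller because more discontinuers are measured. The benefit is fewer outcomes to impute, and it is complete only if those participants attend.
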